2 ELIGIBILITY ASSESSMENT AND ENROLLMENT

2.1 ELIGIBILITY CRITERIA

2.1.1 Inclusion Criteria

- 2.1.1.1 Patients must have histologically confirmed locally recurrent adenocarcinoma of the prostate after prior radiation (EBRT or brachytherapy)
- 2.1.1.2 PSA failure after definitive radiation as defined by the Phoenix criteria (PSA elevation at least 2 ng/dL above post-radiotherapy nadir)
- 2.1.1.3 Age \geq 18 years
- 2.1.1.4 ECOG performance status \leq 2 (Karnofsky \geq 60%, see [Appendix A](#))
- 2.1.1.5 Ability of subject to understand and the willingness to sign a written informed consent document

2.1.2 Exclusion Criteria

- 2.1.2.1 Patients who are receiving any other investigational agents
- 2.1.2.2 PSA \geq 20 ng/dL if no prior DCFPyL scan obtained (If PSA \geq 20 and DCFPyL obtained within 3 months prior to enrollment shows no evidence of metastatic disease, subjects may be included in the study)
- 2.1.2.3 Biochemical recurrence within one year of completion of radiotherapy
- 2.1.2.4 Need for chronic anticoagulation therapy (chronic low dose aspirin is not an exclusion)
- 2.1.2.5 Pre-existing and ongoing radiation-related grade 3 bowel or bladder toxicity
- 2.1.2.6 Inflammatory bowel disease
- 2.1.2.7 Active Lupus or Active scleroderma
- 2.1.2.8 Patients with distant metastatic disease (prostate adjacent adenopathy is not an exclusion)
- 2.1.2.9 Prior prostatectomy
- 2.1.2.10 Subjects with any coexisting medical or psychiatric condition that is likely to interfere with study procedures and/or results
- 2.1.2.11 Subjects with severe claustrophobia that is unresponsive to oral anxiolytics
- 2.1.2.12 Other medical conditions deemed by the Principal Investigator (or associates) to make the subject unsafe or ineligible for protocol procedures
- 2.1.2.13 Subjects weighing $>$ 350 lbs. (weight limit for scanner table), or unable to fit within the imaging gantry
- 2.1.2.14 Serum creatinine $>$ 2 times the upper limit of normal
- 2.1.2.15 Total bilirubin $>$ 2 times the upper limit of normal OR in patients with Gilbert's syndrome, a total bilirubin $>$ 3.0
- 2.1.2.16 Liver transaminases (ALT, AST) greater than 3 times the upper limit of normal
- 2.1.2.17 Patients with positive Human Immunodeficiency Virus (HIV) status and currently

requiring treatment with agents known to sensitize to irradiation, such as protease inhibitors

2.1.3 Recruitment Strategies

Participants will be identified from [name] referral base, largely via screening for 13-C-0119, which includes an arm for locally recurrent prostate cancer after radiotherapy. [name] has developed an excellent professional relationship with numerous referring physicians in the surrounding area who send patients with PSA recurrence after radiotherapy. [name] will expand these efforts. [name] also participates in the RecurRx network, a multi-institutional group evaluation recurrence after radiotherapy. She expects referrals from this source given that she has a therapeutic intervention or these patients. In addition, patients will be recruited from the prostate multidisciplinary clinic.

This protocol may be abstracted into a plain language announcement posted on NIH websites and on NIH social media platforms.

2.2 SCREENING EVALUATION

Note: Screening evaluation testing/procedures are conducted under the separate screening protocol, 01-C-0129 (Eligibility Screening and Tissue Procurement for the NIH Intramural Research Program Clinical Protocols). Assessments performed at outside facilities or on another NIH protocol within the timeframes below may also be used to determine eligibility once a participant has signed the consent.

- Clinical Evaluation: Complete history and physical examination, including weight and performance status within 4 weeks of study entry.
- Laboratory Evaluation: CBC with differential, chemistries (to include creatinine BUN, PSA, testosterone, Alk Phos, ALT, AST, Bilirubin), PT, PTT within 4 weeks of study entry.
- Viral serologies: HIV screening within 4 weeks of study entry
- Radiographic Evaluation: Whole body bone scan, F18 NaF PET, and multiparametric MRI of the prostate. In selected patients, a CT of the abdomen and pelvis (with oral and IV contrast) may also be obtained for staging, particularly if MRI is not felt to adequately have staged the pelvic and abdominal lymph nodes. All imaging studies should be completed within 3 months of study entry. MRI of the prostate obtained more than 3 months (no greater than 5 months prior to entry) may be used if a biopsy has recently been performed, as post-biopsy MRI may not be easily interpretable due to hemorrhage.

2.3 PARTICIPANT REGISTRATION AND STATUS UPDATE PROCEDURES

Registration and status updates (e.g. when a participant is taken off protocol therapy and when a participant is taken off-study) will take place per CCR SOP ADCR-2, CCR Participant Registration & Status Updates found at:

<https://ccrod.cancer.gov/confluence/pages/viewpage.action?pageId=73203825>.

2.3.1 Treatment Assignment Procedures

Cohorts

| Number | Name | Description |
|---------------|---------------|---|
| Cohort 1 | EBRT | Patients with locally recurrent prostate cancer after treatment with EBRT. These patients cannot have had permanent brachytherapy as part of their treatment. |
| Cohort 2 | Brachytherapy | Patients with locally recurrent prostate cancer after treatment with brachytherapy +/- EBRT. These patients must have had brachytherapy as part of their treatment. |

Arms

| Number | Name | Description |
|---------------|--------------------------------|--|
| 1 | Tumor Irradiation | SBRT will be delivered to areas of recurrent prostate cancer identified on imaging and biopsy |
| 2 | Prostate and Tumor Irradiation | SBRT will be delivered to areas of recurrent prostate cancer identified on imaging and biopsy; and a reduced dose will be delivered to the entire prostate |

Treatment Assignment

There is no randomization or stratification on this study.

Subjects in Cohort 1 will be directly assigned to Arm 1.

Subjects in Cohort 2 will be directly assigned to Arm 2.

2.4 BASELINE EVALUATION

- Clinical evaluation: clinical assessment with attention to any new medications or interventions since screening history and physical examination (to be completed within 2 weeks of study entry, screening history and physical examination is acceptable if obtained within the 2-week interval)
- Laboratory evaluation: CBC with differential, BUN, Creatinine, Alk Phos, ALT, AST, Total Bilirubin, PSA, Testosterone, PT, PTT, Hepatitis B, and Hepatitis C (within 4 weeks of study entry)
- 18F-DCFPyL imaging (will not be repeated if performed on a different protocol within 4 months prior to study enrollment).
- Post-Imaging research and diagnostic biopsies of areas in the prostate identified as suspicious and systematic biopsy. If recent systematic biopsies were obtained (within 5 months) systematic biopsies will not be repeated. Fiducial markers to guide radiation

treatment will be implanted simultaneously if not previously placed or visible

- Questionnaires (to be completed prior to treatment and within 2 weeks prior to SBRT). See Section [3.4](#) for further details. Expanded Prostate Cancer Index Composite (EPIC-26), SHIM, AUA-SI, PROMIS Depression SF4a, PROMIS Anxiety SF4a, PROMIS Psychological Impact Positive SF 4a, Decision Regret Scale
- Correlative assays (to be completed prior to treatment and within 2 weeks prior to SBRT). See Section [5.1](#) for further details. Collection of Plasma – three 8 cc EDTA), urine (15cc in a sterile cup), and research biopsies. In patients with active Hepatitis B or C, some research blood work may not be drawn.

3 STUDY IMPLEMENTATION

3.1 STUDY DESIGN

Patients with locally recurrent prostate cancer following radiotherapy will be enrolled in this study if they have no evidence of distant metastatic disease on staging studies. If abnormalities are noted on bone scan and/or NaF PET/CT, the results of these studies will be reviewed by the PI and radiology/nuclear medicine colleagues. On a case by case basis, the likelihood of metastasis will be determined if evidence of abnormalities is visible. In general, NaF PET will be considered more sensitive. Multiparametric MRI of the prostate and 18F-DCFPyL imaging will be obtained to assess for areas of local recurrence. Patients found to have regional adenopathy that is distant to the prostate or metastatic disease at other sites on staging studies such as 18F-DCFPyL will undergo biopsy confirmation if clinically appropriate to confirm metastatic disease and will be removed from the study and replaced if metastases are confirmed. Patients deemed to have a non-metastatic local recurrence will undergo targeted (research and diagnostic) and systematic biopsies of the prostate (diagnostic) to confirm areas of recurrence and correlate imaging with pathology. Areas noted to have uptake on 18F-DCFPyL imaging will also be biopsied if they represent areas not seen on MRI. During the same procedure, fiducials to guide radiotherapy will be placed if not previously placed or visible. Approximately one week after fiducial placement or biopsy (if fiducial placement not required), patients will undergo treatment planning for SBRT.

There will be two Cohorts in this trial. Cohort 1 includes patients with prior EBRT for the treatment of prostate cancer. These patients may have received ADT with EBRT but have not received brachytherapy. Patients enrolled in Cohort 2 will have received brachytherapy of the prostate as a component of the initial radiation treatment (either alone or in combination with EBRT and/or ADT). See section [2.3.1](#).

SBRT will be delivered to areas of recurrent prostate cancer identified on imaging and biopsy (all patients, Arms 1 and 2) and a reduced dose will be delivered to the entire prostate (Arm 2). The low dose total prostate exposure is used in Arm 2 as MR imaging may be moderately compromised in after prior brachytherapy.

Table 2: Dose Levels

| | Arm 1: Tumor Irradiation | | Arm 2: Prostate and Tumor Irradiation | |
|-------------------|---------------------------------|----------------------|--|----------------------|
| Dose level | Dose to prostate | Dose to tumor | Dose to prostate | Dose to tumor |
| Level 1 | - | 40 Gy | 30 Gy | 40 Gy |
| Level 2 | - | 42.5 Gy | 30 Gy | 42.5 Gy |
| Level 3* | | 45 Gy | 30 Gy | 45 Gy |

* As of amendment version dates 4/13/2021 and 10/12/2021, determination has been made not to escalate to dose level 3 for both arms. Refer to section [1.2.5](#).

3.1.1 Dose Limiting Toxicity

Dose-limiting toxicities will be defined as follows (during treatment and within the first three weeks after treatment):

- Grade 3 rectal, small bowel, or urinary toxicity that does not resolve to Grade 2 or less within 4 days with appropriate medical management
- Other grade 3 in-field toxicities attributable to SBRT that do not resolve to Grade 2 or less within 4 days with appropriate medical management
- Delays of more than one week in completing radiation treatment due to toxicity (cumulative duration of delay over the course of the entire treatment).

Additionally, late toxicities (those that occur after 90 days following completion of treatment) will be followed and scored but will not be used for escalation with the following exception.

If Grade ≥ 4 late bowel or Grade ≥ 3 bladder injury is observed in 2 patients in any cohort, dose escalation will be terminated in that arm and the dose below that dose level in which the toxicity was observed will be considered the MTD. The criteria for late DLT for bladder were changed to Grade 3 to Grade 4 via amendment version date 04/13/2021, and should apply retroactively to all prior participants. MTD will be determined for each arm separately. Early and late toxicities used for assessment of DLTs should be attributable (possible, probable or definite) to SBRT. Changes in sexual and erectile function will not be considered a DLT.

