Abbreviated Title: SBRT for Recurrent Prostate Ca

Version Date: 05/24/2023

Abbreviated Title: SBRT for Recurrent Prostate Ca

NIH Protocol #:17-C-0153

Version Date: 05/24/2023

NCT Number: NCT03253744

Title: Phase I Trial of Image Guided Focally Dose Escalated Prostate SBRT for Locally Recurrent Prostate Cancer after Prior Radiotherapy

NCI Principal Investigator: [name].
Radiation Oncology Branch
National Cancer Institute
[name]
[name]
[name]
[contact]
E-mail: [contact]

| | |
|---------------|--------------------|
| Drug Name: | 18F-DCFPyL |
| IND Number: | 133631 |
| Sponsor: | NCI CCR |
| Manufacturer: | NIH PET department |
| Supplier | NIH PET department |

Commercial Agents: Radiation

PRÉCIS

Background:

- Prostate cancer that recurs after prior radiation treatment can be challenging to cure due to the side effects of available treatments such as surgery and cryoablation.
- Re-irradiation with brachytherapy or stereotactic approaches has shown excellent rates of prostate cancer disease control with tolerable side effects.
- Using image guidance to allow highly conformal focal re-irradiation may potentially increase the efficacy of re-irradiation.

Objectives:

- Define the maximum tolerated dose (MTD) of image guided, focally dose escalated prostate radiation with stereotactic body radiation therapy (SBRT) in patients with a local recurrence of prostate cancer after prior radiotherapy.

Eligibility:

- Histological confirmation of recurrent prostate cancer after prior irradiation (external beam or brachytherapy)
- No evidence of distant metastases of prostate cancer
- No prior prostatectomy
- Subject is ≥ 18 years old
- ECOG performance status ≤ 2 (Karnofsky $\geq 60\%$)

Design:

- This is a Phase I trial of focal dose escalation with SBRT using image and pathologic guidance.
- Areas in the prostate shown to have tumor on biopsy or with advanced imaging studies will be treated with highly conformal SBRT over a period of two to three weeks. Treatment will be guided and gated by fiducials implanted in the prostate.
- Patients will be treated to escalating doses based on tolerability of the treatment.
- Quality of life and functional outcomes such as urine, bowel, and erectile function will be assessed with questionnaires.
- Up to 46 patients will be enrolled.

TABLE OF CONTENTS

| | |
|---|----|
| PRÉCIS..... | 2 |
| TABLE OF CONTENTS | 3 |
| STATEMENT OF COMPLIANCE | 8 |
| 1 INTRODUCTION | 9 |

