1.2.5 Study MTD Determination/Dose Expansion

Arm 1 (Amendment Version Date 4/13/2021)

At dose level 1, only mild radiation related AEs have occurred with no PSA recurrence of the as of yet. At dose level 2, 2 participants in arm 1 have had some significant urine toxicity (Grade 3 hematuria, transient and Grade 3 urinary incontinence) that do not meet the protocol endpoint for maximum tolerated dose (MTD).

Since no one has failed at dose level 1 and the toxicity was less significant, the protocol has been amended to change the criteria for late DLT to Grade 3 urinary toxicity (instead of Grade 4), which would allow us to consider dose level 1 as MTD in Arm 1, trigger expansion at that cohort, and halt dose escalation. These changes would reduce the risk to participants.

Arm 2 (Amendment Version Date 10/12/2021)

Determination has been made to expand dose level 2 for arm 2. Three patients have been treated at dose level 1 and three patients have been treated at dose level 2 (one is currently undergoing treatment). Toxicity has not exceeded grade 2 urinary or grade 3 bowel. Of all 5 patients in this arm who have completed treatment, there is no evidence of recurrence.

Based on recent accumulating literature from the definitive treatment setting (no prior radiation), it is clear that further escalation of dose may have long term toxicity. Thus, in the face of excellent disease control, we feel it would be inappropriate to increase dose further as it will expose patients to risk without additional benefit.

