3.1.2 Dose Escalation

Dose escalation will proceed in parallel in Arm 1 (Tumor Irradiation) and Arm 2 (Prostate and Tumor Irradiation) in groups of 3–6 patients. The MTD is the dose level at which no more than 1 of up to 6 patients experience DLT during treatment and up to 3 weeks following completion of treatment, and the dose below that at which at least 2 (of ≤ 6) patients have DLT as a result of treatment. If a patient did not experience DLT and did not finish treatment, he will not be evaluable for toxicity and will be replaced in the dose level (See [Table 2](#)).

Dose escalation will follow the rules outlined in [Table 3](#) below for each Arm (1 or 2) independently as MTD and toxicities are expected to be different as a result of prior treatment.

Table 3: Escalation Decision Rule

| Number of Patients with DLT at a Given Dose Level | Escalation Decision Rule |
|---|--|
| 0 out of 3 | Enter up to 3 patients at the next dose level |
| ≥ 2 | Dose escalation will be stopped. This dose level will be declared the maximally administered dose (highest dose administered). Up to three (3) additional patients will be entered at the next lowest dose level if only 3 patients were treated previously at that dose. |
| 1 out of 3 | Enter up to 3 more patients at this dose level. 
• If 0 of these 3 patients experience DLT, proceed to the next dose level.• If 1 or more of this group suffer DLT, then dose escalation is stopped, and this dose is declared the maximally administered dose. Up to three (3) additional patients will be entered at the next lowest dose level if only 3 patients were treated previously at that dose. |
| ≤ 1 out of 6 at highest dose level below the maximally administered dose | This is the MTD and is generally the recommended phase 2 dose. 6 additional patients may be entered at the recommended phase 2 dose. |

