3.8.4 Treatment Delivery

An SBRT set up will be used for all treatments. Treatment will be delivered in 5 fractions over a span of 7-14 days. Image guidance will include pre-treatment cone beam CT as per standard of care. An additional post-treatment cone beam CT after each fraction will be obtained to assess intrafraction motion. Calypso beacons will be utilized for real time tumor tracking as per the standard of care if implanted.

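### Section 3.1.1 does not count an acute Grade 4 toxicity as a DLT if it settles within 4 days, unless it also delays SBRT by more than a week

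*Combined protocol and SAP*

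**What the plan says.** Section 3.1.1 sets three acute DLT criteria, which apply during treatment and for three weeks after it. The first is "Grade 3 rectal, small bowel, or urinary toxicity that does not resolve to Grade 2 or less within 4 days with appropriate medical management". The second bullet uses the same single grade and the same 4-day allowance for any further toxicity inside the treated field that SBRT may have caused. The third carries no grade: "Delays of more than one week in completing radiation treatment due to toxicity", where all interruptions are summed.

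Events must be possibly, probably or definitely attributable to SBRT. The only place in 3.1.1 that names Grade 4 or uses a greater-or-equal sign is the late rule. That rule concerns toxicity after 90 days and acts only when 2 patients are affected.

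No other section adds an acute Grade 4 or 5 criterion. Section 10.4.4 refers back to 3.1.1, as does the toxicity item in 3.10.1. Section 10.4.1 speaks of unacceptable toxicity without defining it. Under 3.1.2 and Table 3, a level with no more than 1 DLT in up to 6 patients is acceptable and 2 or more is too many.

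**The concern.** A DLT definition should not treat a more severe event more leniently than a milder one. Here a Grade 3 urinary event lasting five days is a DLT, while a Grade 4 urinary event that drops to Grade 2 on day three need not be. The 4-day allowance suits Grade 3. Nothing in the text confines it to Grade 3 once the bullets are read to include higher grades.

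The acute rule also fits poorly with the sponsor's own late rule. Late bladder injury of Grade 3 or higher counts with no allowance for resolution. Section 1.2.5 lists a transient Grade 3 hematuria among the events that led to that change.

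At stake is the primary endpoint. The MTD decision rests on very small counts, so one unclassified event can move a level from too toxic to acceptable. DLT reporting, a secondary endpoint, uses the same definition.

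**Working it through.** The plan gives no figure to reproduce. The check runs test cases through the three bullets under two readings.

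**1. Which reading is likelier.** The greater-or-equal sign in the late rule favors reading the acute bullets literally. Against that, the protocol elsewhere uses bare Grade 3 as a threshold. Section 1.2.5 describes the late urinary criterion as Grade 3, where 3.1.1 writes Grade 3 or higher. Section 2.1.2 excludes "Pre-existing and ongoing radiation-related grade 3 bowel or bladder toxicity", which can hardly mean that Grade 4 is admissible. Grade 3 or higher was probably meant.

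**2. Test cases** (attributable, inside the acute window, total delay of one week or less):

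| Event | Literal Grade 3 | Grade 3 or higher |
|---|---|---|
| Grade 3, at Grade 2 or less by day 3 | not a DLT | not a DLT |
| Grade 3, still above Grade 2 after 4 days | DLT | DLT |
| Grade 4, at Grade 2 or less by day 3 | not a DLT | **not a DLT** |
| Grade 4, unresolved after 4 days | not named | DLT |
| Grade 5 | not named | DLT |

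If the delay exceeds one week, the third bullet makes the event a DLT on either reading. The third row is the gap that survives both readings.

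**3. Reach of the delay bullet.** It cannot act after the last fraction. During treatment it misses any event after which SBRT is completed with no more than a week's total delay. Section 3.8.4 says "Treatment will be delivered in 5 fractions over a span of 7-14 days", and the window runs 21 days beyond that:

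- 7 days of treatment: 21/(7+21) = 0.75
- 14 days: 21/(14+21) = 0.60
- 21 days, the upper end of the two to three weeks in the précis: 21/(21+21) = 0.50

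These are shares of calendar time, not of events.

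**4. Consequence for the rule.** One uncounted event turns 2 of 6 (exceeds the MTD) into 1 of 6 (acceptable).

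**5. Illustration only, all rates assumed.** If a fraction q of patients had such an event, the chance of at least one in six is 1 − (1 − q)^6:

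- q = 0.5%: 0.030
- q = 1%: 0.059
- q = 2%: 0.114
- q = 5%: 0.265

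The chance of seeing no more than 1 DLT in 6 at rate p is (1 − p)^6 + 6p(1 − p)^5. Suppose part of the true rate goes uncounted:

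| True rate p | All counted | 0.5 points uncounted | 5 points uncounted |
|---|---|---|---|
| 17% | 0.729 | 0.741 | 0.844 |
| 25% | 0.534 | 0.546 | 0.655 |
| 33% | 0.358 | 0.368 | 0.464 |
| 40% | 0.233 | 0.241 | 0.319 |

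The increase is 0.8 to 1.2 percentage points at the low assumption and 8.6 to 12.1 at the high one. The high one is demanding: 5 points is 29% of all DLTs at p = 17% (0.05/0.17) and 12.5% at p = 40% (0.05/0.40).

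**The case against.** The strongest reply is that the gap is narrow and comes late. It needs an attributable Grade 4 event that drops at least two grades in 4 days and costs no more than a week of treatment. The documents describe no such event. The one Grade 4 toxicity they mention is a hemorrhagic cystitis leading to cystoprostatectomy, among 29 patients in the prior SBRT series (section 1.2.1). Its timing is not given, and nothing suggests it was brief. Escalation is closed in both arms, Arm 1 on late urinary toxicity and Arm 2 on outside literature and good disease control. Weekly team review (7.4.1), SAE reports within 24 hours (8.3) and possible suspension for unacceptable risk (12.1) also protect patients. Investigator discretion in 3.10.1 allows removal from therapy however a DLT is worded.

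Most of this stands and limits the weight of the point. It does not close the gap, because none of these safeguards makes the event a DLT or enters it in Table 3.

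Two stronger inferences should be resisted. A reader might conclude that toxic deaths go uncounted. That follows only from the literal reading, which is probably not the intended one, and even then not for a death preceded by persistent Grade 3. Read as Grade 3 or higher, a death cannot resolve and so counts.

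A reader might also conclude that a patient who stops SBRT for such an event leaves the denominator, because 3.1.2 says: "If a patient did not experience DLT and did not finish treatment, he will not be evaluable for toxicity and will be replaced". The documents do not settle this. Never finishing can be read as a delay of more than a week, and 6.3.1 and 10.3 keep everyone who starts SBRT evaluable for toxicity. That is a separate ambiguity and not part of this point.

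**Conclusion.** The acute DLT definition is wrong as written. On either reading, an attributable acute Grade 4 event that resolves to Grade 2 or less within 4 days is not a DLT unless it also brings more than one week of cumulative delay. Read literally, persistent Grade 4 and Grade 5 events are not named either.

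The documents do not support saying that a past dose decision was mistaken. Section 1.2.5 reports no Grade 4 event: only mild radiation-related events at level 1 in Arm 1, two Grade 3 urinary events at level 2 in Arm 1, and nothing above Grade 2 urinary or Grade 3 bowel in Arm 2. That account dates from the 2021 amendments and does not cover patients treated since.

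The remaining effect is on the no-more-than-1-of-6 criterion at the retained levels and on DLT reporting. Its size cannot be estimated from the documents. The percentages under step 5 rest wholly on assumed rates and show only how sensitive a six-patient rule is to a missed event.

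**What to change.** Amend 3.1.1 in three ways:

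1. Keep the 4-day resolution allowance for Grade 3 only.
2. Add that any Grade 4 or 5 rectal, small bowel, urinary or other in-field toxicity attributable to SBRT, arising on treatment or in the following three weeks, is a DLT whether or not it resolves.
3. State that this applies retroactively to all prior participants, as 3.1.1 already does for the late bladder criterion.

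Sections 3.10.1 and 10.4.4 follow by reference. The cost is a short amendment and a look back at acute toxicity grades already collected; no new data are needed. The downside is that a brief Grade 4 event would now count, which makes the rule slightly more conservative.

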10.1 STATISTICAL HYPOTHESIS

- Primary Endpoint: Define the maximum tolerated dose (MTD) of image-guided, focally dose escalated prostate SBRT in patients with a local recurrence of prostate cancer after prior radiotherapy. Assessment of toxicities for dose escalation will occur through 3 weeks after SBRT.
- Secondary Endpoints:
 - Define the dose-limiting toxicities and toxicity profile of image-guided, focally dose escalated prostate SBRT in patients previously treated with radiotherapy. Assessment of toxicities for dose escalation will occur through 3 weeks after SBRT.

- Describe the rate of PSA control (biochemical progression free survival, bPFS) at 1 and 2 years after treatment with focally dose escalated SBRT for locally recurrent prostate cancer after irradiation. We hypothesize that the rate of PSA control (bPFS) will compare favorably to the 75% rate obtained with brachytherapy in several previously published series.
- Describe the effects of focally dose escalated prostate SBRT on patient reported outcomes (SHIM, AUA Symptom Index, EPIC-26) in patients previously treated with radiotherapy. We hypothesize a reduction in quality of life (urinary and gastrointestinal side effects) after re-irradiation that persists for several months but returns to baseline in most patients by 2 years after treatment. We hypothesize that erectile dysfunction will progress after reirradiation without improvement over time.
- Evaluate 18F-DCFPyL imaging as a method to detect locally recurrent prostate cancer after radiation. We hypothesize that 18F-DCFPyL will have a high positive predictive value and sensitivity for diagnosing recurrent prostate cancer.

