10.4 STATISTICAL ANALYSES

10.4.1 General Approach

This is a phase I study. There are two arms to this study for 1) patients with prior brachytherapy as a component of their treatment for prostate cancer, and 2) patients with prior EBRT without brachytherapy. Arms are enrolled and escalated separately. Groups of 3-6 patients are evaluated at each dose level. The dose level on which 2 patients experience unacceptable toxicity is considered to have exceeded the MTD. The next lower dose level on which no more than 1/6 patients experience unacceptable toxicity is considered the MTD for each arm of the study.

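### A Grade 4 bowel injury confined to days 22-90 after SBRT, or a Grade 5 bowel event in that interval, counts toward neither MTD rule, and the time window for bladder injury is unclear

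*Combined protocol and SAP*

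**What the plan says.** Section 3.1.1 has two rules.

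- **Acute rule.** Toxicity is dose-limiting if it arises "during treatment and within the first three weeks after treatment". For bowel or urinary events the criterion is Grade 3 that has not fallen to Grade 2 or less within 4 days. Section 3.1.2 ties the MTD to patients who "experience DLT during treatment and up to 3 weeks following completion of treatment", and section 10.1 repeats the limit: "Assessment of toxicities for dose escalation will occur through 3 weeks after SBRT".
- **Late rule.** "late toxicities (those that occur after 90 days following completion of treatment) will be followed and scored", but they do not affect escalation unless an exception is met: "If Grade ≥ 4 late bowel or Grade ≥ 3 bladder injury is observed in 2 patients in any cohort". In that case escalation stops in the arm and the next lower dose becomes the MTD. The following sentence begins "The criteria for late DLT for bladder were changed", so it treats the bladder criterion as a late one.

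Both rules require at least possible attribution to SBRT. Section 10.4.1 adds, without a time limit, that "The dose level on which 2 patients experience unacceptable toxicity is considered to have exceeded the MTD". Section 3.10.1 defines unacceptable toxicity by pointing back to 3.1.1. Section 6.1 has adverse events documented to 90 days. Table 3 in section 3.1.2 allows an expansion: "6 additional patients may be entered at the recommended phase 2 dose". According to section 1.2.5, Arm 1 expands at level 1 and Arm 2 at level 2.

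**The concern.** The MTD is the primary endpoint, and the two rules that fix it do not meet. One ends at day 21 and the other begins after day 90. A Grade 4 or 5 bowel event between them is recorded but changes nothing, while the same event after day 90 would count toward lowering the dose. The plan gives no reason for treating the interval differently.

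Bladder injury raises a second problem. In the exception, the word *late* stands before bowel only, so on a literal reading Grade 3 or higher bladder injury counts at any time. The next sentence calls it a late criterion, and on that reading days 22-90 are excluded for bladder too. Two careful readers could score the same patient differently.

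What is at stake is the Arm 2 expansion at 42.5 Gy. If the two-patient rule applies to expansion patients, two such bowel injuries on days 22-90 would leave that dose standing, whereas the same two injuries after day 90 would set the MTD at 40 Gy.

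**Working it through.** The plan states no figure on this point, so there is none to reproduce. The first two steps compare rules; the third is an illustration.

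**1. Coverage by day after SBRT.** The windows are those of sections 3.1.1, 3.1.2 and 10.1. The acute criteria are written for Grade 3; I assume that they include higher grades.

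| Grade 4 bowel injury (start-end day) | Acute rule (start by day 21) | Late rule (after day 90) |
|---|---|---|
| 21-30 | in window | no |
| 22-30 | no | no |
| 22-90 | no | no |
| 60-120 | no | yes if presence counts, no if onset counts |
| 91-100 | no | yes |

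The uncovered interval is 90 - 22 + 1 = 69 days. A Grade 5 event cannot resolve, but one that falls in the interval meets neither window either.

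**2. Does another section close the gap?**

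- Section 10.4.1 has no window of its own, but its key term leads through 3.10.1 back to 3.1.1.
- Section 6.1 requires recording to day 90. A parenthetical remark there links that collection to the MTD, which hints at intent, but the section sets no counting rule.
- Section 7.4.1 bases enrolment and escalation decisions on earlier patients' toxicity, and section 12.1 allows suspension. Neither gives a grade, a count or a window.

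None of these supplies a criterion for days 22-90.

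**3. Size, for the bowel limb only.** The documents give no rate for bowel injury of Grade 4 or higher on days 22-90, so the per-patient rate q is an assumption. The number of patients n at Arm 2 level 2 is taken two ways:

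- n = 3 + 6 = 9: the three patients treated at that level when expansion was decided (section 1.2.5), plus six in expansion.
- n = 6 + 6 = 12: a full dose level plus six in expansion (Table 3).

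The chance of at least two uncounted injuries is

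P = 1 - (1 - q)^n - n q (1 - q)^(n - 1).

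For q = 0.05 and n = 9: 1 - 0.6302 - 0.2985 = 0.071. For q = 0.05 and n = 12: 1 - 0.5404 - 0.3413 = 0.118.

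| q (assumed) | n = 9 | n = 12 |
|---|---|---|
| 0.5% | 0.09% | 0.16% |
| 1% | 0.34% | 0.6% |
| 2% | 1.3% | 2.3% |
| 5% | 7.1% | 11.8% |

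I attach no figure to the bladder limb. On the literal reading no qualifying bladder event is missed. On the late-only reading the size depends on how many events fall on days 22-90. The 7% rate of Grade 3 or higher genitourinary toxicity (2 of 29) in the earlier SBRT series in section 1.2.1 is not split by that interval.

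**The case against.** The strongest reply is that little remains to be decided. Level 3 is closed in both arms. Arm 1 expands at the lowest level, so no lower dose is available there. In Arm 2, section 1.2.5 reports nothing above Grade 3 bowel or Grade 2 urinary toxicity, with no time limit on that statement, when expansion was chosen. The team has also acted on toxicity that did not meet the rule: two Grade 3 urinary events in Arm 1 led it to amend the criteria and halt escalation. All of this stands, and it confines the point to patients treated later in the Arm 2 expansion. It does not supply a rule for them. The Arm 1 response took an amendment, and discretion is not an MTD criterion.

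Three further replies also have force.

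- **The rates are unanchored.** The largest figures need a 5% rate of bowel injury of Grade 4 or higher within 69 days, which nothing in the documents supports. At 0.5% to 1% the chance stays below 1%.
- **The rule may not reach expansion patients.** It is written as an exception about escalation, which has ended. The contrast between 42.5 and 40 Gy is therefore conditional, and the plan should say which is meant.
- **Injury persisting past day 90 is a lesser matter.** The plan does not say whether onset or presence counts, and the 3-month visit (90 ± 7, about days 83-97) straddles the border. But the exception turns on injury being observed, and late toxicities are followed and scored, so an injury still present after day 90 fits the wording reasonably well.

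A reader might infer that a severe event has already been missed, or that the Arm 1 MTD rests on events that should not have counted. The documents support neither. They report no event in the gap, and section 1.2.5 gives no onset dates for the two urinary events.

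**Conclusion.** The point holds as a gap in a stated primary-endpoint rule. Followed exactly, sections 3.1.1, 3.1.2 and 10.1 leave an attributable Grade 4 bowel injury confined to days 22-90, or a Grade 5 bowel event in that interval, out of the MTD count. The bladder window is ambiguous rather than clearly open.

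The practical size is small. It concerns patients in the Arm 2 level 2 expansion, and matters for the dose only if the two-patient rule is meant to cover them. The percentages show scale under assumed rates and 9 or 12 patients; the ceiling of 21 evaluable patients per arm in section 10.2 might allow more. It would be too strong to say that either chosen dose is wrong: on the toxicity in section 1.2.5 neither changes. The case for acting is that the correction is cheap and makes the safety rule clear.

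**What to change.** Amend section 3.1.1 as follows.

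- Apply the two-patient exception to any attributable bowel injury of Grade 4 or higher, or bladder injury of Grade 3 or higher, whose qualifying grade is first reached after the 3-week acute window. The date of that grade is needed because section 10.4.4 codes each event once at maximum severity, and an event may start at a lower grade inside the acute window.
- State that this covers both limbs and the expansion patients.
- For days 22-90, keep the acute rule's 4-day resolution condition for Grade 3 bladder events. Otherwise a transient event would be treated more strictly on day 22 than on day 20.
- Align sections 3.1.2, 10.1 and 10.4.1.
- Tabulate other in-field events of Grade 3 or higher on days 22-90 by onset. Persistent Grade 3 bowel toxicity in that interval stays outside the MTD count, and the table makes it visible.

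The cost is a short amendment and a re-score from adverse event dates already collected to day 90, with a source check where a grade rose after onset. There are no new visits and no longer wait between cohorts. The downside is a post hoc clarification of a primary-endpoint rule, following the retroactive bladder change of 04/13/2021; the report should disclose it as such.
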